8.4 Stopping Rules

The stopping rules specified below are based on the knowledge available at study development. The stopping rule applies to the overall study. We note that the Adverse Event Stopping Rule may be adjusted in the event of either (1) the study re-opening to accrual or (2) at any time during the conduct of the trial and in consideration of newly acquired information regarding the adverse event profile of the treatment(s) under investigation. The study team may choose to suspend accrual because of unexpected adverse event profiles that have not crossed the specified rule below.

Accrual will be temporarily suspended to this study if at any time we observe events considered at least possibly related to study treatment (i.e. an adverse event with attribute specified as "possible", "probable", or "definite") that satisfy the following:

• If 2 or more patients in the first 6 treated patients (or 30% after the first 6 treated patients have been accrued) experience a grade 3 or higher non-hematologic adverse event.

We note that we will review grade 4 and 5 adverse events deemed "unrelated" or "unlikely to be related", to verify their attribution and to monitor the emergence of a previously unrecognized treatment-related adverse event.

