1.1 Background

Deucravacitinib (BMS-986165) is an oral selective inhibitor of tyrosin kinase 2 (TYK2), a member of the Janus kinase (JAK) family. Deucravacitinib (BMS-986165) binds to the regulatory domain of TYK2 (also known as pseudokinase domain) to stabilize an inhibitory interaction between the regulatory and the catalytic

domains of the enzyme. This results in allosteric inhibition of receptor-mediated activation of TYK2 and its downstream activation of Signal Transducers and Activators of Transcription (STATs). JAK kinases, including TYK2, function as pairs of homo- or heterodimers in the JAK-STAT pathways. TYK2 activates STAT-dependent gene expression and functional responses of interleukin (IL)-12, IL-23, and type I interferon (IFN) receptors. IL-12 promotes Th1 differentiation in T-cells and enhances the production of IFN gamma ¹. IL-23 is an inflammatory cytokine that stimulates development and differentiation of Th17 cells via activation on STAT3. Subsequently, Th17 cells secrete inflammatory mediators, including IL-17 and TNF-alpha ². IL-23 also exerts its effects on dendritic cells and macrophages to stimulate production of IL-1, IL-6, and TNF-alpha.

Deucravacitinib (BMS-986165) represents a therapeutically attractive drug by inhibiting these cytokine pathways. This study is aimed at evaluating the effects of Deucravacitinib (BMS-986165) 6 mg twice daily (Cohort A) in subjects with Lichen Planopilaris (LPP). Our preliminary results of Deucravacitinib (BMS-986165) 6 mg BID (Cohort A) improved disease activity by the LPPAI and PGA at weeks 12 and 16. In addition, clinical signs and symptoms were improved at 3-4 months and was well tolerated.

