Lichen Planopilaris (LPP) is a form of lymphocyte-mediated scarring alopecia. It presents as discrete patches with characteristic perifollicular erythema and scale involving the scalp. LPP is histopathologically characterized by lichenoid inflammation at the infundibular portion of hair follicle. Cell-mediated cytotoxicity is the main pathogenetic mechanism in lichenoid tissue reactions and the maintenance and progression of chronic cytotoxic inflammation requires IFN gamma signaling. Disease progression results in permanent alopecia and is associated with negative quality of life impacts including depression and anxiety. There are no on-label or effective remittive treatments. Conventional topical (e.g. corticosteroids) and systemic immunosuppressives (e.g. mycophenolate mofetil) used in the treatment of LPP directly inhibit lymphocytes but generally cannot induce clinical remission ³. Therefore, there remains a critical unmet need for alternative therapeutic options to treat LPP.

Cutaneous LP is characterized by Type I and Type II IFN driven cell mediated cytotoxic immune response that is highly responsive to JAK1, 2 inhibitions ⁴⁻⁶. However, unlike LP, LPP is a chronic, scarring condition. The etiology of LPP as well as the scarring is poorly understood; however, Th17 cells are thought to play a critical role in this process. In line with the role of Type I & II IFNs and Th17 cells in LPP, more moderate responses are seen with to JAK 1, 2 inhibition ^{7 8,9}. Taken together, we believe that TYK2 inhibition has the potential to treat the inflammation of LPP as well as the scarring generated by Th17 stimulated fibroblasts.

We additionally propose a multi-center, exploratory, open-label, single-arm design study using Deucravacitinib (BMS-986165, systemic TYK2 inhibitor for the treatment of LPP with 6 mg orally QD (Cohort B) to assess safety and efficacy.

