Temporary Interruption of Investigational Product: In some circumstances, patients may need to temporarily interrupt treatment as a result of AEs or abnormal laboratory values that may have an unclear relationship to investigational product. For the abnormal laboratory findings and clinical events (regardless of relatedness), specific guidance is provided for temporarily interrupting treatment and when treatment may be restarted. Retest frequency and timing of follow up laboratory tests to monitor the abnormal finding is at the discretion of the investigator. Investigational product that was temporarily interrupted because of an AE or abnormal laboratory value may be restarted at the discretion of the investigator.

- Absolute Neutrophil Count (ANC): Treatment should be interrupted if ANC < 1 x 109 cells/L and may be restarted once ANC return above this value
- Absolute Lymphocyte Count (ALC): Treatment should be interrupted if ALC < 0.5 x 109 cells/L and may be restarted once ALC return above this value
- Hemoglobin (Hb): Treatment should be interrupted if Hb < 8 g/dL and may be restarted once Hb return above this value
- Hepatic transaminases: Treatment should be temporarily interrupted if drug-induced liver injury is suspected

Permanent Discontinuation from Investigational Product: Investigational product must be permanently discontinued if the patient or the patient's designee requests to discontinue investigational product. Discontinuation of the investigational product for abnormal liver tests should be considered by the investigator when a patient meets 1 of the following conditions:

- ALT or AST >8 x ULN
- ALT or AST >5 x ULN for more than 2 weeks after temporary interruption of investigational product
- ALT or AST >3 x ULN and total bilirubin level (TBL) >2 x ULN or international normalized ratio (INR) >1.5
- ALT or AST >3 x ULN with the appearance of fatigue, nausea, vomiting, right upper quadrant pain or tenderness, fever, rash, and/or eosinophilia (>5%)

- ALP >3 x ULN that is deemed to be of liver origin and drug-related
- ALP >2.5 x ULN and TBL >2 x ULN
- ALP >2.5 x ULN with the appearance of fatigue, nausea, vomiting, right upper-quadrant pain or tenderness, fever, rash, and/or eosinophilia (>5%)
- Investigational product should be permanently discontinued if any of the following laboratory abnormalities are observed:
- White blood cell count $<1000 \text{ cells}/\Box L (1.00 \text{ x } 103/\Box L \text{ or } 1.00 \text{ billion}/L)$

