- ANC $<500 \text{ cells}/\Box L (0.50 \text{ x } 103/\Box L \text{ or } 0.50 \text{ billion}/L)$
- Lymphocyte count $<200 \text{ cells}/\Box L (0.20 \text{ x } 103/\Box L \text{ or } 0.20 \text{ billion/L})$
- Hemoglobin < 6.5 g/dL (< 65.0 g/L)

Hepatitis B virus DNA testing will be performed in enrolled patients who tested positive for HBcAb at screening. Patients who are HBcAb-positive and HBV DNA-negative (undetectable) at Visit 1 will require HBV DNA monitoring every 3 months and at the patient's last visit, regardless of their hepatitis B surface antibody (HBsAb) status. The following actions should be taken in response to HBV DNA test results:

- If a single result is obtained with a value "below limit of quantitation," the test should be repeated within approximately 2 weeks.
- If the repeat test result is "target not detected," monitoring may resume according to the study schedule.
- If the patient has 2 or more test results with a value "below limit of quantitation" during the study, HBV DNA testing should be performed approximately once per month for the remainder of the study and referral to a hepatologist is recommended.
- If a result is obtained with a value above limit of quantitation at any time during the study, the patient will be permanently discontinued from investigational product and should be referred to a hepatology specialist immediately

Supplemental 1: Appropriateness of Measures

Skin Scoring:

LPPAI

Disease activity in LPP can be measured with the well validated Lichen Planopilaris Activity Index, first developed in 2010. LLPAI quantifies LPP activity using the following variables: itch, pain, burn, scalp erythema, perifollicular erythema, perifollicular scaling, pull test, and spreading.

PGA

The use of PGA is well validated in other inflammatory skin conditions and is frequently used as a primary or secondary endpoint assessment tool. The assessment measures the overall response to treatment as assessed by the physician.

Itch Scoring:

The VAS, VRS, NRS and Skindex-16 are all well validated measure of itch. The VAS, VRS and NRS scores focus on a gestalt of itch. The Skindex-16 scoring system focuses on itch and its impact upon quality of life.

Supplemental 2: Safety Measures

Baseline Screening:

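### The only mandatory accrual pause (section 8.4) never counts related cytopenias, even those severe enough to stop drug permanently under section 8.1: a low-priority wording gap

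*Combined protocol and SAP*

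**What the plan says.** Section 8.4 contains one criterion that obliges the team to suspend accrual. It counts patients who "experience a grade 3 or higher non-hematologic adverse event", provided the event is at least possibly related to study treatment. The limit is 2 or more of the first 6 treated patients, then 30%. On scope, the section states: "The stopping rule applies to the overall study".

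Three other provisions of 8.4 bear on the point:
- The team "may choose to suspend accrual because of unexpected adverse event profiles" that have not crossed the rule.
- The rule may be adjusted at any time in the light of new safety information.
- Grade 4 and 5 events judged unrelated or unlikely to be related will be reviewed to check their attribution.

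Section 8.1 deals with the individual patient and has two tiers for blood counts:
- **Interruption.** For example, "Treatment should be interrupted if ANC < 1 x 109 cells/L". There are similar limits for lymphocytes (0.5 x 10^9/L) and hemoglobin (8 g/dL).
- **Permanent stop.** "Investigational product should be permanently discontinued if any of the following laboratory abnormalities are observed". The limits are WBC <1000, ANC <500 and lymphocytes <200 cells/uL, and hemoglobin <6.5 g/dL.

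Section 1.6 says that the drug can suppress blood-cell growth, calls the risk low, and promises monitoring. Table 3 schedules a CBC at every visit. The documents give no reason for leaving hematologic events out of the 8.4 count.

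**The concern.** Several patients could lose study drug permanently because of treatment-related neutropenia, lymphopenia or anemia while the 8.4 count stayed at zero. The plan would act on each patient but would not be obliged to stop and review before enrolling the next one.

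There is also an asymmetry within 8.4. An unrelated grade 4 neutropenia is promised an attribution review. A related one gets neither that review nor a place in the count.

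At stake is whether a review before further exposure is automatic or depends on the team choosing to act. This is an open-label study in which the sponsor-investigator oversees safety. The efficacy estimate and the sample size are not affected.

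**Working it through.** **Reading the text.** Of the provisions in 8.4, only the non-hematologic criterion compels a pause. The suspension for unexpected profiles is optional, the adjustment clause is optional, and the grade 4-5 review covers unrelated or unlikely events and is not a pause. Related cytopenias thus contribute nothing to the mandatory trigger, whatever their frequency.

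**Size.** The plan states no operating characteristic for the rule, so there is no figure to reproduce.

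Inputs from the documents: 22 patients (section 3.2); limit of 2 in the first 6, then 30% (section 8.4). Inputs assumed: all event rates, because the documents give none.

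Method: exact recursion with independent patients and a look after each patient, each outcome taken as known at once. Accrual pauses the first time the count reaches 2 for n up to 6, or the smallest whole number at or above 0.30n afterwards. That is 3 at n = 7-10, 4 at 11-13, 5 at 14-16, 6 at 17-20 and 7 at 21-22.

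Hand check of the first-six part at a 5% rate: 1 - 0.95^6 - 6 x 0.05 x 0.95^5 = 1 - 0.7351 - 0.2321 = 0.0328, or 3.3%. Continuing to 22 patients gives 3.7%.

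*Hematologic events alone, counted from patient 1 over 22 patients:*

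| Assumed hematologic rate | Pause, rule as written | Pause, if counted |
|---|---|---|
| 1% | 0 | 0.15% |
| 2% | 0 | 0.60% |
| 5% | 0 | 3.7% |
| 10% | 0 | 14.1% |
| 20% | 0 | 47.6% |

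*Cost in extra pauses, with an assumed 5% non-hematologic rate.* The per-patient chance of either kind of event is r = 1 - (1 - 0.05)(1 - p), where p is the hematologic rate:

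| p | r | Pause over 22 patients |
|---|---|---|
| 0% | 0.05 | 3.7% (the present rule, at any p) |
| 1% | 1 - 0.95 x 0.99 = 0.0595 | 5.2% |
| 5% | 1 - 0.95 x 0.95 = 0.0975 | 13.5% |

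*How much the count could still do now.* Section 1.1 reports week 12 and 16 results for Cohort A ("Our preliminary results of Deucravacitinib (BMS-986165) 6 mg BID (Cohort A) improved disease activity") and then introduces Cohort B ("We additionally propose a multi-center, exploratory, open-label, single-arm design study"). How many Cohort A patients have been treated, and with what events, is not stated. Suppose all 12 were event-free. The pooled count would then need 6 of the first 6-8 Cohort B patients, or 7 of 9-10. The chance from hematologic events alone is 0.003% at a 10% rate and 0.16% at 20%. After 6 event-free patients it is 0.7% and 8.0%.

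**The case against.** The strongest reply is that nothing is contradictory. Section 8.1 governs dosing of one patient and 8.4 governs accrual, and no principle requires every dosing limit to feed an accrual rule. Section 1.6 calls the blood-count risk low and lists no cytopenia among its common or serious reactions. The risks it does list, such as infection, rhabdomyolysis and liver enzymes, count if related and grade 3 or higher. A related grade 3 infection following a cytopenia would count too.

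Other safeguards are also real: CBC at each visit, the 8.1 limits, SAE reporting to the funder within 24 hours or one business day, reporting to the IRB and FDA, and regular assessment of SAEs under 8.5. A cluster of severe cytopenias would probably be noticed.

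Most of this stands, and it is why the priority is low. It does not close the gap. The safeguards either protect one patient, inform others, or leave the pause to choice.

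Three stronger readings are tempting and not supported:
- **That the study has no study-level protection against cytopenias.** It has the optional suspension. Although that clause speaks of unexpected profiles and cytopenia is a named risk, the definition of unanticipated problems in 8.1 includes greater frequency or severity than expected.
- **That every 8.1 interruption limit should count.** Those limits are reversible dosing guidance, and the documents give no basis for making each one an accrual event.
- **That Cohort B must have its own limit.** Cohort B takes half the daily dose of Cohort A (section 5.2), and the dilution argument rests on an assumed number of event-free Cohort A patients. Running such a limit beside the pooled one raises the chance of a pause from 3.7% to 7.2% at a 5% non-hematologic rate with no hematologic events at all. Dilution affects non-hematologic events equally, so it is a separate question.

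**Conclusion.** The gap is real and narrow. Related cytopenias that end a patient's treatment under 8.1 can never trigger the only mandatory accrual pause, and no reason is given. It is a low-priority matter of safety wording. It is not an error in the analysis.

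If the risk is as low as section 1.6 says (1-2% assumed), counting these events from patient 1 would cause a pause in under 1% of trials. The clause matters only if that belief is wrong.

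Three limits apply:
- Every rate is an assumption.
- Outcomes are treated as known immediately, although treatment lasts 24 weeks and accrual spacing is not given. The chance of crossing is therefore not the amount of exposure averted.
- If most of Cohort A has already been treated without events, the pooled count would rarely trigger in what remains of the study.

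**What to change.** In section 8.4, count once per patient, toward the existing limit of 2 in the first 6 and then 30%, any at-least-possibly-related hematologic event that meets an 8.1 permanent-discontinuation limit or is grade 4 or higher. The grade clause covers platelets, for which 8.1 has no limit. Name the 8.1 limits in the text so that the count does not depend on whether a laboratory value was first recorded as an adverse event under Supplemental 3. If the exclusion is deliberate, a sentence giving the reason would be the alternative.

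The change is wording only and needs no new test. Its price is more temporary pauses, as tabulated above. A separate Cohort B limit is not part of this change. The sponsor may weigh one on its own merits.

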It is unknown whether TYK2 inhibition may be associated with the observed or potential adverse reactions of JAK inhibition. Higher rates of all-cause mortality, including overall thrombosis, deep venous thrombosis, and pulmonary embolism were observed in patients treated with a JAK inhibitor compared to those treated with TNF blockers in rheumatoid arthritis (RA). Deucravacitinib (BMS-986165) is not approved for use in RA. While we do not expect such events to occur, patients should seek medical advice if they experience signs or symptoms of DVT/PE, such as significant shortness of breath, bloody cough, or lower leg swelling, redness, or pain.

Rhabdomyolysis and Elevated CPK

Treatment with Deucravacitinib (BMS-986165) has been associated with an increased incidence of asymptomatic creatine phosphokinase (CPK) elevation and rhabdomyolysis compared to treatment with placebo. Discontinue if markedly elevated CPK levels occur or myopathy is diagnosed or suspected. Patients should promptly report any unexplained muscle pain, tenderness or weakness, particularly if accompanied by malaise or fever.

Cancer Risk:

Deucravacitinib (BMS-986165) may have the potential to affect the subject's immune system; they may be at increased risk for infections. Cancers, including lymphomas, were observed in a few patients in the Deucravacitinib clinical studies; the role of Deucravacitinib in these cancers is uncertain. Long term safety evaluations are ongoing.

Vaccines:

Live vaccines should not be given concurrently with Deucravacitinib (BMS-986165).

Pregnancy Risk:

The effect of the study drug on a fetus (developing baby still in the womb), or on a breastfeeding infant, is unknown. Because of these risks, women cannot take part in this study if they are pregnant.

Lactation Risk:

There are no data on the presence of Deucravacitinib (BMS-986165) in human milk, the effects on the breastfed infant, or the effects on milk production. Deucravacitinib is present in rat milk. When a drug is present in animal milk, it is likely that the drug will be present in human milk. Because of the risks, women cannot take part in this study if they are breastfeeding.

Skin biopsy:

A skin biopsy is generally a safe procedure, but some potential risks may include local pain, mild local bruising, bleeding, scarring, and an infection at the site where the skin biopsy was performed. If a topical antibiotic is used afterwards, then there is a small risk of an allergic reaction.

Blood draw:

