8.5 Medical Monitoring

It is the responsibility of the Principal Investigator to oversee the safety of the study at his/her site. This safety monitoring will include careful assessment and appropriate reporting of adverse events as noted above, as well as the construction and implementation of a site data and safety-monitoring plan (see section 10 "Study Monitoring, Auditing, and Inspecting"). Medical monitoring will include a regular assessment of the number and type of serious adverse events.

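### The accrual-suspension rule in 8.4 counts events from grade 3, but its check on events called unrelated or unlikely starts at grade 4

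*Combined protocol and SAP*

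**What the plan says.** Section 8.4 temporarily suspends accrual if 2 or more of the first 6 treated patients, or 30% after that, "experience a grade 3 or higher non-hematologic adverse event". Only events attributed as possible, probable or definite count.

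The same section then adds a check on the other attributions: "We note that we will review grade 4 and 5 adverse events deemed" unrelated or unlikely to be related, with verification of the attribution as its first stated purpose. Its second stated purpose is to watch for a treatment-related event not previously recognised. The team may also suspend accrual for unexpected adverse event profiles that have not reached the threshold.

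Section 8.5 opens with a general duty: "This safety monitoring will include careful assessment and appropriate reporting of adverse events as noted above". The next sentence sets the periodic review: "Medical monitoring will include a regular assessment of the number and type of serious adverse events". Later in 8.5, any detected adverse event is to be followed until it resolves or is judged permanent, and its severity and suspected relationship to the drug are reassessed at each visit.

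Sections 8.2, 8.3 and 9.3 add follow-up of each event, evaluation by the sponsor-investigator and review of study data by the principal investigator.

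**The concern.** The verification exists because attribution decides which events the rule counts. Its floor, grade 4, lies one grade above the rule's floor, grade 3, and no reason is given. A grade 3 event called possible counts towards suspension. The same event called unlikely does not count, and 8.4 does not provide for anyone to verify that call.

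Attribution is made in an open-label, single-arm study with no control rate to calibrate it. Section 1.6 says that the drug "has been associated with an increased incidence of asymptomatic creatine phosphokinase (CPK) elevation and rhabdomyolysis compared to treatment with placebo" and describes CPK and liver-enzyme increases as dose-related. A laboratory event can be severe by grade without being serious, so the SAE tally need not capture it.

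The rule is the only numeric study-level safety threshold in the plan, and early on it turns on two patients. One uncorrected label can decide whether it is met.

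**Working it through.** **1. Which stated check reaches an event called unrelated or unlikely?**

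| Check | Grade 4–5 | Grade 3, serious | Grade 3, non-serious |
|---|---|---|---|
| Attribution verification (8.4) | yes | no | no |
| Regular tally of serious events (8.5) | if serious | yes | no |
| Per-visit reassessment of relationship (8.5) | yes | yes | yes |

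The last column has one entry. That reassessment stops at resolution or permanence. After week 4 the visits in Table 3 are four weeks apart, so a transient event may resolve before the next one. It also works within one patient, whereas the second purpose of the 8.4 review needs a view across patients.

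**2. How much could it matter?** The plan states no operating characteristic for the rule, so there is no figure to reproduce. Inputs from the documents are the threshold (8.4) and 22 subjects (3.2). Inputs that are assumptions:
- p, the true rate of related non-hematologic events of grade 3 or higher, taken as the same for all patients although there are two dose cohorts;
- m, the share of qualifying events called unrelated or unlikely and never corrected.

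The rate the rule sees is q = p(1 − m). For the first 6 patients:

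P(2 or more of 6) = 1 − (1 − q)^6 − 6q(1 − q)^5

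- p = 0.30, m = 0: q = 0.30; 1 − 0.1176 − 0.3025 = 0.580
- p = 0.30, m = 0.20: q = 0.24; 1 − 0.1927 − 0.3651 = 0.442
- p = 0.30, m = 0.40: q = 0.18; 1 − 0.3040 − 0.4004 = 0.296

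For all 22 patients, an exact patient-by-patient recursion suspends at 2 or more within the first 6, or when the cumulative count divided by n is at least 0.30 for n = 7 to 22. That requires 3 patients at n = 7–10, 4 at 11–13, 5 at 14–16, 6 at 17–20 and 7 at 21–22.

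| p | m | q | First 6 | Over 22 |
|---|---|---|---|---|
| 0.30 | 0 | 0.30 | 0.580 | 0.790 |
| 0.30 | 0.20 | 0.24 | 0.442 | 0.616 |
| 0.30 | 0.40 | 0.18 | 0.296 | 0.404 |
| 0.20 | 0 | 0.20 | 0.345 | 0.476 |
| 0.20 | 0.20 | 0.16 | 0.247 | 0.332 |
| 0.20 | 0.40 | 0.12 | 0.156 | 0.199 |

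At p = 0.10 and m = 0.20 (q = 0.08), the first-6 probability moves only from 0.114 to 0.077.

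**3. Why these are upper figures.** The model exposes every qualifying event to uncorrected misattribution. Grades 4 and 5 are already verified, serious grade 3 events are tallied, and every open event is reassessed at visits. Suppose only half of qualifying events were exposed, with 20% of those mislabelled. The overall share is then 0.5 × 0.20 = 0.10, so q = 0.30 × 0.90 = 0.27. The probabilities become 0.513 in the first 6 and 0.710 over 22, against 0.580 and 0.790.

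**The case against.** A reader might infer that a mislabelled grade 3 event is never looked at again, or that monitoring covers serious events only. The documents contradict both. Section 8.5 requires careful assessment of adverse events generally and per-visit reassessment of relationship with no limit on grade or seriousness. Sections 8.2, 8.3 and 9.3 add further investigator review. Only the periodic tally is confined to serious events.

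Other points on that side have weight:
- The definition of possible in 8.3.1 includes events that another cause could also explain, so a plausible alternative for a CPK or liver-enzyme rise does not by itself remove it from the count.
- The interruption guidance in 8.1 applies regardless of relatedness, so individual protection does not rest on attribution alone.
- The 8.4 review also covers hematologic events, which the rule excludes. Its scope was never identical to the rule's, and a different floor is not in itself an error.
- The team may suspend accrual below the threshold.
- The 8.4 review is not described as independent, so extending it asks the same people to re-read their own calls.

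These points rule out the stronger readings but leave a gap. If routine reassessment were sufficient, the grade 4–5 verification would not be needed either. Follow-up under 8.2 can end at resolution alone. The discretionary suspension is worded for unexpected profiles, and CPK and liver-enzyme rises are already described in 1.6.

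**Conclusion.** The mismatch is plain in the text: the rule counts from grade 3, and its attribution check starts at grade 4. No other section gives a grade 3 event called unrelated or unlikely the verification that 8.4 describes.

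It would go too far to conclude that the rule under-triggers. That requires misattribution to occur and to survive the per-visit reassessment, and the documents give no rate for either. If both happen, the direction is downward. At an assumed true rate of 30% with 20% of all qualifying events mislabelled, the drop is from 0.58 to 0.44 in the first 6 patients. That is an upper illustration; it shrinks when fewer events are exposed, and in absolute terms is much smaller at a true rate of 10%. The point is a cheap improvement to safety monitoring, not a demonstrated failure of the rule.

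**What to change.** Three wording changes:

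1. In 8.4, extend the attribution review from grades 4 and 5 to every adverse event of grade 3 or higher called unrelated or unlikely.
2. In 8.4, state that an event re-attributed to possible or higher enters the suspension count.
3. In 8.5, have the regular assessment also tally events of grade 3 or higher, serious or not, so that a pattern across patients can be seen.

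No threshold, dose or patient-management rule changes. The cost is a few more events for the same team to review in a study of 22 patients. The limitation is that the reviewers are not independent of the original attribution, so some bias may remain.
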